### **13.8 Follow-Up 3: Post-Colonoscopy Procedure**

Subject will be telephoned by study site to assess subject satisfaction with the colonoscopy procedure as compared to the C-Scan. Follow up window is 1-3 days post-colonoscopy. Additionally, the BBPS and colonoscopy report will be collected from the test site for comparative analysis with the C-Scan procedure. The subject will be exited from the study upon completion of this follow-up

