### 12.2 Inclusion Criteria

- a. Male or female at the age of 40-80 years' old.
- b. Subject provided signed informed consent.
- c. Subject is willing and able to comply with the specified study requirements and follow-up evaluations, and can be contacted by telephone.
- d. Subjects able and agrees to undergo colonoscopy procedure.
- e. BMI  $\geq 19$  and  $\leq 35$ .
- f. Maximum body (abdominal) circumference  $< 120$  cm.
- g. Has at least 3 bowel movements per week
- h. A colonoscopy procedure is pre-scheduled within 60 days

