## 13 STUDY PROCEDURES AND SCHEDULE

### 13.1 Study Procedures

The C-Scan study procedures and flow are outlined in Figure 3. The schedule of study assessments are listed in Table 1. The subjects are only required to attend two visits, but are expected to conduct phone assessments after ingestion but prior to expulsion of the capsule.

*Table 1: Schedule of Assessments*

Assessments	Pre-screening	Visit 1: Baseline and C-Scan	Follow-up 1: C-Scan - During Procedure follow-up	Follow-Up 2: C-Scan Procedure End follow-up Call	Follow-up 3: Colonoscopy Post Procedure follow-up Call
Visit Window	-30-0 days	0 days	0- As required days	1-3 days post procedure	1-3 days post procedure
Questionnaire	X				
Informed Consent		X			
Inclusion/ Exclusion Criteria		X			
Demographics		X			
Medical History		X			
Concomitant Medications		X			
Pregnancy test 		X			
C-Scan procedure		X			
Connect to C-Scan		X			
C-Scan capsule		X			
Ingest contrast		X	X		
FIT test			X		
Follow up phone calls 			X		
Capsule Excretion				X	
Abdominal x-ray 				X	
Subject Satisfaction Survey				X	X
Boston Bowel Preparation Scale (BBPS)					X
Colonoscopy Report	X 				X
Follow up visit call				X	X
Adverse Events		X	X	X	
Study Exit					X

[figure not shown]
Urine pregnancy test for women of childbearing potential

Minimum of two phone calls per day until capsule excretion

Abdominal x-ray ONLY if suspected that capsule has not been excreted (subject will come to office/unscheduled visit)

Collection of a previous colonoscopy report, if available

	Document Title	Clinical Investigational Plan For Study CL-SY-02-0096		
	Document No.	DOC001593	Revision	03

	Document Title	Clinical Investigational Plan For Study CL-SY-02-0096		
	Document No.	DOC001593	Revision	03

Figure 3: Study Procedure Flow Chart

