## 16 ADVERSE EVENTS

Subjects will be carefully monitored for adverse events. Subjects will be guided to report if they feel any pain or discomfort during the trial. At each visit or phone contact, subjects will be asked if they experienced any adverse reaction since the last visit.

Any adverse events with an onset following beginning of bowel preparation to colonoscopy procedure will not be collected. Colonoscopy related adverse events are not part of the study, are considered standard of care and will not be reported.

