## **16.4 Safety Reporting Procedures**

### **16.4.1 Adverse Events Reporting**

Subjects are encouraged to report any event to the study team and consult the PI for any change in their well-being. Subjects will be asked for any change in their medical condition during each study visit or phone call with the exception of Visit 2 for the standard of care Colonoscopy and the associated preparation procedure.

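### The protocol contradicts itself on whether adverse events are asked about at Follow-up 3, the last contact, so events starting between Follow-Up 2 and bowel preparation may be missed

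*Combined protocol and SAP*

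**What the plan says.** Some parts of the protocol leave the question out of Follow-up 3:

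- The adverse-event row in Table 1 (section 13.1) reads "Adverse Events X X X". The marks stand under Visit 1, Follow-up 1 and Follow-Up 2, and the Follow-up 3 cell is empty. The schedule in section 5 has the same row.
- Section 13.8 gives the call its purpose: "Subject will be telephoned by study site to assess subject satisfaction with the colonoscopy procedure as compared to the C-Scan". It then lists the BBPS and the colonoscopy report, and ends: "The subject will be exited from the study upon completion of this follow-up".

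Other parts require it:

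- Section 16: "At each visit or phone contact, subjects will be asked if they experienced any adverse reaction since the last visit".
- Section 16.4.1 repeats the rule for each visit or call, "with the exception of Visit 2 for the standard of care Colonoscopy and the associated preparation procedure".
- Section 11.1 describes a well-being call after the C-Scan procedure and applies the same follow-up after colonoscopy.

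Two further statements fix the interval at issue. Section 16 ends collection by onset: "Any adverse events with an onset following beginning of bowel preparation to colonoscopy procedure will not be collected". Section 12.2 sets the time to colonoscopy: "A colonoscopy procedure is pre-scheduled within 60 days".

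**The concern.** The primary outcome (section 10.3) is the incidence of device- or procedure-related SAEs. The count depends on subjects being asked consistently over the whole period in which an event is eligible. That period runs to the start of bowel preparation, but the last contact with a marked adverse-event item is Follow-Up 2, one to three days after the capsule procedure. The only later routine contact is Follow-up 3, and the protocol gives two different instructions for it.

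A site that builds its call script from the schedule and section 13.8 would rely on subjects volunteering an event in that interval. A site that follows sections 16 and 16.4.1 would ask. With up to two sites, ascertainment of the primary outcome could differ between them, and a question left out can lower the count but not raise it.

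**Working it through.** **1. Is there another prompt in the interval?** The calls made at least twice daily stop at capsule excretion (Table 1 footnote). The adverse-event question in the usability questionnaire (section 13.7.2) is answered once the capsule procedure is over, so it does not reach forward. No routine contact is scheduled between Follow-Up 2 and colonoscopy. Follow-up 3 is therefore the only scheduled chance to ask.

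**2. Is the interval meant to be collected?** Yes. The section 16 cut-off removes only onsets after bowel preparation begins.

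**3. Does the 16.4.1 exception settle it?** No. It names Visit 2, the colonoscopy and its preparation. Visit 2 is not a column in either schedule, and the Follow-up 3 call is not mentioned. A site could read the exception as extending to the post-colonoscopy call, although the wording does not say so.

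**4. How long is the interval?** First, a check on the plan's own figure. Colonoscopy at day 60 plus 1 to 3 days to Follow-up 3 gives 61 to 63 days, and 61/7 = 8.7 weeks to 63/7 = 9.0 weeks. This lies inside the 8 to 10 weeks of participation in section 11.2. It is consistent with the 60 days running from Visit 1 but does not establish it.

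Inputs for the gap:

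- Colonoscopy at day 60 from Visit 1 (section 12.2; the start of the count is not stated, so this is an assumption).
- Transit time T: mean 52.3 h (section 8.1). The range 24 to 100 h that section 7.2 gives for the colon is used here as short and long total times.
- Follow-Up 2 call F: 1 to 3 days after the procedure (Table 1).
- Bowel preparation P: not stated; assumed 1 to 2 days.

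Gap = 60 − T/24 − F − P.

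| Transit | F = 1, P = 1 | F = 3, P = 2 |
|---|---|---|
| 24 h | 60 − 1.0 − 1 − 1 = 57.0 d (8.1 wk) | 60 − 1.0 − 3 − 2 = 54.0 d (7.7 wk) |
| 52.3 h | 60 − 2.2 − 1 − 1 = 55.8 d (8.0 wk) | 60 − 2.2 − 3 − 2 = 52.8 d (7.5 wk) |
| 100 h | 60 − 4.2 − 1 − 1 = 53.8 d (7.7 wk) | 60 − 4.2 − 3 − 2 = 50.8 d (7.3 wk) |

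With colonoscopy at day 30 and mean transit, the gap is 30 − 2.2 − 3 − 2 = 22.8 days to 30 − 2.2 − 1 − 1 = 25.8 days.

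**5. What does one missed event weigh?** If all 45 subjects are analysed, exact (Clopper-Pearson) limits give:

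- 0/45 = 0%, two-sided 95% upper limit 1 − 0.025^(1/45) = 7.9%.
- 1/45 = 2.2%, 95% CI 0.06% to 11.8%.

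One event is the difference between reporting no related SAE and reporting one, and it moves the upper limit by about 4 percentage points (11.8 − 7.9 = 3.9).

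**The case against.** The strongest objection is that the protocol already requires the question. Follow-up 3 is a phone contact, section 16 applies to every phone contact and looks back to the last visit, 16.4.1 repeats the rule, and 11.1 adds a well-being follow-up after colonoscopy. Section 13.8 does not claim to be an exhaustive list. The blank cell may simply reflect the decision not to collect events after preparation begins. This stands against one inference a reader might draw from the schedule, namely that the protocol decides not to ask about the interval. The documents do not support that; they support a contradiction. What remains is that nothing in them says whether the schedule or the text governs, and leaving the question out is a foreseeable reading.

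A second objection is that late related events are unlikely. Most listed capsule risks belong to its passage, the radiation risk ends at excretion (section 15.1.4), and frequent calls cover retention while the capsule is known to be inside. This largely stands and limits the size of the point. It is not complete. Section 13.7.1 lets an auditory end signal close the procedure, section 15.1.3.1 accepts that a capsule may remain after a positive indication, and section 15.1.1 lists erosion of the colon mucosa as a risk.

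Third, subjects are encouraged to report any event unprompted (16.4.1), and the case report forms are not among the documents, so a difference between sites is a possibility rather than a fact. Both statements are correct. Spontaneous reporting is still weaker than a scheduled question.

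**Conclusion.** The point holds as an internal contradiction about ascertainment of the primary outcome. Sections 5, 13.1 and 13.8 leave adverse events out of the exit call, while sections 16 and 16.4.1 require the question and 11.1 supports it. The interval affected is at most about 7 to 8 weeks, given colonoscopy on day 60 from Visit 1 and one to two days of preparation. An earlier colonoscopy shortens it.

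A reader might go further and infer that most of the eligible period is unobserved, or that the related-SAE rate is biased downward by a known amount. Neither follows. The gap is calendar time without a prompt under one of two readings, not a count of lost events, and no figure in the documents gives the rate of related SAEs after excretion. The number missed is unknown and probably small. Only the direction is certain: any miss lowers the count. The correction is worth making before sites write their call scripts.

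**What to change.** - Mark Adverse Events at Follow-up 3 in the section 5 schedule and in Table 1.
- Add to section 13.8: At this call, ask about any adverse event with onset between Follow-Up 2 and the start of bowel preparation.
- Record the date and time bowel preparation started on the case report form, so that each event can be placed on the correct side of the section 16 cut-off.
- State in 16.4.1 that the exception for Visit 2 does not cover the Follow-up 3 call for those earlier onsets.

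The cost is two table cells, two sentences and one case report form entry, using a call that already takes place. The rule against collecting later onsets is unchanged. The downside is that a few more events may be recorded.

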### **13.9 Unscheduled Visit(s)**

After 100 hours following Capsule ingestion, if the subject is unaware of the excretion of the capsule, or if it suspected that the capsule has not been excreted naturally, the subject will call the site to determine options for excretion. They may be asked to return to the investigative site for an abdominal x-ray to see if the capsule remains in the body. If so, measures will be taken by site personnel to ensure capsule excretion. See Capsule Retention section below.

### **13.10 C-Scan Analysis**

Upon return of the capsule to the investigational site, the capsule data will be downloaded from the "Track" and validated for completeness by the technical team. Next, the raw data will be transformed to 3D format ('reconstruction') by the View workstation and optionally, selected bookmarks will be prepared for the Viewers.

The files will be transferred to designated centralized reading center (may be located outside the United States) and reviewed by three trained medical reviewers for clinical analysis and preparation of procedure subject report. Each reviewer will generate a final report including 'per patient' recommendations.

	Document Title	Clinical Investigational Plan For Study CL-SY-02-0096		
	Document No.	DOC001593	Revision	03

Decision on presence/absence of polyps will be determined by majority.

C-Scan findings will be compared to the FIT results and to the study Optical Colonoscopy procedure.

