### 10.4 Secondary Outcome Measures

- Subject compliance will be assessed by
  - Non-compliance rate throughout the study via diary completion by the subject Specific questionnaire completed by remote subject monitoring (via telephone)
- Subject satisfaction will be established by:
  - Designated questionnaire that focuses on patient's impressions regarding tolerance and potential safety concerns. Acceptance criteria was defined as average score >3.5 (1- low satisfaction to 5- high satisfaction), which represent high satisfaction with the safety and tolerance of the C-scan system.
  - Comparing patient's satisfaction with colonoscopy procedure.
- Collecting procedure related data:
  - Technical performance in normal daily routine.
  - Segmental transit time.
  - Procedure duration.
  - Bowel movements.
  - Agreement between C-Scan and colonoscopy with respect to the presence/absence of colonic polyp(s) [Note: C-scan data not to be used for clinical decision making in the care of patients, for this clinical study].
  - Inter-observer variability in the detection of significant clinical findings on a 'per patient' decision
- Battery life Assessment
  - Assessing adequate power supply for complete scan of the colon: length of capsule operation lifetime with respect to the lifetime specification of 100 +/- 10% hours.
- Device performance
  - Assessing colon model by the physician reviewers as presented on C-Scan View (e.g., normal, partial, right side missing, etc.).
  - Collecting data to improve the product's algorithm.

	Document Title	Clinical Investigational Plan For Study CL-SY-02-0096		
	Document No.	DOC001593	Revision	03

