### 13.5 Visit 1: Baseline

Upon completion of the informed consent process, subject's eligibility will be assessed against the Inclusion and Exclusion criteria. Previous reports of optical or virtual colonoscopy should be collected and kept with the subject's file.

If the subject does not meet the inclusion/exclusion criteria, they will be considered a screen failure and excluded from the analysis.

The following information will be collected at this visit:

- General medical history and concomitant medication will also be assessed and documented.
- Subject's demographic and baseline information will be assessed and documented, including: date of birth, gender, height, weight, belly circumference, prior abdominal surgery, GI symptoms, and reason for referral.
- If applicable, documentation of previous GI procedures, such as optical colonoscopy

	Document Title	Clinical Investigational Plan For Study CL-SY-02-0096		
	Document No.	DOC001593	Revision	03

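### Section 13.10 does not blind readers or bookmark preparers or secure independent reads, so reader variability can be understated and agreement with colonoscopy can be inflated

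*Combined protocol and SAP*

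**What the plan says.** Section 13.10 sets out the reading chain. The technical team checks the downloaded data, the View workstation reconstructs it, and "optionally, selected bookmarks will be prepared for the Viewers". The files go to a central reading center, where they are "reviewed by three trained medical reviewers for clinical analysis and preparation of procedure subject report". Each reader writes a final per-patient report. "Decision on presence/absence of polyps will be determined by majority", and "C-Scan findings will be compared to the FIT results and to the study Optical Colonoscopy procedure".

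Two secondary outcomes in section 10.4 rest on this chain. One is the agreement of C-Scan with colonoscopy on whether polyps are present. The other is "Inter-observer variability in the detection of significant clinical findings on a 'per patient' decision".

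The results that could inform a read are collected elsewhere in the plan:

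- **Prior reports.** Section 13.5: "Previous reports of optical or virtual colonoscopy should be collected and kept with the subject's file".
- **FIT.** Section 13.6.1 has the result reported to the study team before or during the capsule procedure.
- **Study colonoscopy.** Section 13.8 collects the report for comparison with C-Scan, and section 17.1 has procedure reports, with the colonoscopy report as the example, passed to the sponsor in de-identified form.

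**The concern.** A measure of inter-observer variability is meant to show how far readers differ when each works alone. If all three receive the same marked locations, part of their agreement is agreement with whoever or whatever placed the marks. Because bookmarks are optional and no rule says when they are used, marked and unmarked cases would also be mixed within at most 45 subjects.

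The second issue is distinct. Agreement with colonoscopy is informative only if the C-Scan call was made without knowledge of the colonoscopy or of results that predict it. Section 11.1 admits people whose polyps were already found and who are referred for polypectomy; for them a prior report says much about the reference result. Section 12.2 requires a colonoscopy scheduled within 60 days and section 13.10 sets no deadline for reading, so a read can come after the colonoscopy report.

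At stake is whether these two secondary results can be taken at face value when the device's reading performance is described.

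**Working it through.** **Text check.** The plan states no agreement figure derived from inputs, so there is nothing to reproduce. Against each safeguard, the text gives:

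| Safeguard | What the text gives |
|---|---|
| Who selects bookmarks, and by what rule | Not stated |
| When bookmarks are used | Optional, no rule |
| Independent reads | Separate final reports (13.10); independence not stated |
| Blinding to FIT, prior reports, study colonoscopy | Not stated for readers or preparers |
| Reads locked before the colonoscopy report | Not stated; the capsule procedure precedes colonoscopy (11.1), but the reading has no deadline |

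**Illustration: inputs.** Section 8.1 reports positive and negative percent agreement of 44% and 89% in the prior study, and 65% of subjects with polyps. Using 0.44 and 0.89 as the sensitivity and specificity of a single reader is an assumption. Prevalence is 0.65 or, by assumption, 0.30. A third, wholly assumed setting is prevalence 0.50, sensitivity 0.60 and specificity 0.85. Let w be the share of each reader's calls that follow one shared bookmark call of the same accuracy, and u the share set by knowing the reference result. Both are assumed.

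**1. Shared bookmarks and reader agreement.** For two independent reads at prevalence 0.30:

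- Observed agreement: 0.30(0.44² + 0.56²) + 0.70(0.89² + 0.11²) = 0.7151
- Positive rate: 0.30 × 0.44 + 0.70 × 0.11 = 0.209
- Chance agreement: 0.209² + 0.791² = 0.6694
- Kappa: (0.7151 − 0.6694)/(1 − 0.6694) = 0.138

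Two readers who both follow the bookmark (probability w²) always agree; otherwise agreement is as for independent reads. Hence kappa(w) = w² + (1 − w²) × kappa(0).

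| Setting (prevalence; sensitivity/specificity) | w = 0 | 0.25 | 0.50 | 0.75 |
|---|---|---|---|---|
| 0.30; 0.44/0.89 | 0.138 | 0.192 | 0.354 | 0.623 |
| 0.65; 0.44/0.89 | 0.113 | 0.168 | 0.335 | 0.612 |
| 0.50; 0.60/0.85 | 0.216 | 0.265 | 0.412 | 0.657 |

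A simulation of 400,000 cases with three readers and Fleiss' kappa matches the first two rows to within 0.003. Reader accuracy does not change along a row, because the bookmark was given the readers' own accuracy.

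**2. Agreement of the majority call with colonoscopy.** For three independent reads, each correct with probability s, the majority is correct with probability M(s) = 3s²(1 − s) + s³.

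- Independent and blinded: M(0.44) = 0.410 and M(0.89) = 0.966.
- Shared bookmark, w = 0.50: positive 0.44 × M(0.72) + 0.56 × M(0.22) = 0.44 × 0.8087 + 0.56 × 0.1239 = 0.425; negative 0.89 × M(0.945) + 0.11 × M(0.445) = 0.89 × 0.9913 + 0.11 × 0.4178 = 0.928.
- Knowledge of the reference: s becomes u + (1 − u) × 0.44 for positives, and likewise with 0.89 for negatives. At u = 0.25, M(0.58) = 0.619 and M(0.9175) = 0.981.

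| Mechanism | Positive agreement | Negative agreement |
|---|---|---|
| Neither | 0.410 | 0.966 |
| Bookmarks only, w = 0.25 / 0.50 / 0.75 | 0.415 / 0.425 / 0.435 | 0.954 / 0.928 / 0.902 |
| Knowledge only, u = 0.10 / 0.25 / 0.50 | 0.494 / 0.619 / 0.809 | 0.973 / 0.981 / 0.991 |

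So bookmarks mainly raise agreement between readers, and knowledge of results mainly raises agreement with colonoscopy.

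**The case against.** The best defense is that the plan already provides some separation. The files sent to the reading center appear to be the reconstructed capsule data, and 13.10 mentions no clinical reports going with them. Prior reports stay in the subject's file, FIT results go to the study team, and each reader writes a separate report. This makes exposure less likely. It is not a blinding rule, and it does not cover bookmark preparers or the order of reading. A reading-center charter may supply what is missing, but the available text cites none. The note in 10.4 that C-Scan data do not guide care restricts clinicians and does not blind readers.

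A second defense is that bookmarks may be part of the intended reading workflow, so that bookmark-aided variability is a legitimate quantity. That stands, provided bookmarks are applied by one rule and the results are labelled as aided.

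Third, little hangs on these outcomes: this is an unpowered pilot (14.1.1) with descriptive analysis (14.1.4). That stands too and limits the weight of the point.

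Several stronger readings are tempting but not supported:

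- That variability will be understated. Bookmarks are optional; if none are prepared, this mechanism has no effect.
- That bookmarks alone inflate agreement with colonoscopy. From a blinded preparer they barely move positive agreement and lower negative agreement in the illustration.
- That dependent reads always weaken a majority vote. This fails where single-read accuracy is below 50%: at 0.44 an independent majority reaches only 0.410, and dependence raises it slightly.
- That inflation could carry the study past a pass mark. The 55% target in 8.1 belongs to the prior study; this plan sets no criterion for agreement.

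**Conclusion.** The point holds as a gap in safeguards with two distinct consequences. Where bookmarks are used, the three reads are not independent and inter-observer variability can be understated. If readers or preparers know the FIT, prior or study colonoscopy results, agreement with colonoscopy can be inflated. The documents do not show that either will happen.

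The sizes are illustrative. With half of calls following a bookmark, kappa rises by about 0.20 to 0.22 across the three settings. With a quarter of calls set by the reference, majority positive agreement rises by about 0.21 (0.619 − 0.410). Both rest on assumed following and leakage rates and on borrowed or assumed reader accuracy. The leakage figure supposes knowledge of the reference itself; FIT or a prior report would reveal it only in part.

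The affected outcomes are secondary and descriptive. The primary outcome, related SAEs (10.3), is untouched. The change is still worth making before reading starts, because blinding cannot be restored afterwards.

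**What to change.** Amend section 13.10 to state that:

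1. Bookmark preparers and readers are blind to FIT, prior colonoscopy reports and the study colonoscopy.
2. Each reader independently locks a per-patient decision before any unblinding.
3. Inter-observer variability is computed from decisions locked without bookmarks.
4. If bookmarks are part of the intended workflow, a named role prepares them by one stated rule for all cases, and bookmark-aided majority and agreement results are reported separately.

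The cost is protocol wording and, where bookmarks are used, a second look by the same three readers: at most 45 × 3 = 135 reader-cases. No extra subjects or readers are needed. Reported agreement may be lower.
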